Nurse-led intervention to minimise adverse drug reactions for older adults in care homes: a quality improvement process intervention

Introduction

Medicines' management is an area where innovation could improve delivery and outcomes of care and reduce unnecessary costs. However, widespread weaknesses in the monitoring and management of adverse drug reactions (ADRs) or side-effects, which can sometimes be fatal, means that preventable ADRs are responsible for 5-8% unplanned hospital admissions in the UK, costing the NHS £1.5-2.5bn pa (NICE 2015) – figures unchanged in the last decade. Between 2005 and 2013, 18% of 13,699 primary care patient safety incident reports, and 24% of 996 reports describing serious harm or fatalities were attributed to prescription medicines, particularly avoidable ADRs, mainly due to inadequate monitoring, communication or decision-making (Carson-[name] 2016). Most ADRs are due to poor monitoring, not poor prescribing (Gabe 2011). These problems persist, despite new guidelines, computerised reminders, safety initiatives, and medication reviews, intimating the need for innovation.

Up to 50% of people in care homes are over-prescribed medicines, and many doses are too high, particularly for mental-health medicines (Banerjee 2009). ADRs can be life-threatening (e.g. haemorrhage, falls, cardiac arrhythmias, renal failure), debilitating (e.g. drug-induced Parkinsonism, ataxia, postural hypotension) or subtle, and mistaken for signs of ageing or underlying conditions. They can be overlooked, leading to hospitalisation, behaviour problems, loss of comfort and dignity (Howard et al 2007, Jordan 2008, Jordan et al 2014; Jordan et al 2015).

Polypharmacy presents a major threat to the patient safety of older adults internationally. There is widespread consensus that over-prescribing and failure to monitor are the underlying culprits (Banerjee 2009; Gabe et al 2011). However, there is less consensus as to how routine care should change to address inappropriate prescribing and suboptimal medicines' management.

Currently, there is no comprehensive, systematic assessment of problems potentially related to prescribed medicines, and doses are not regularly reviewed (Jordan et al 2016). Our intervention (Jordan et al 2014; Jordan et al 2015) offers a solution. We are seeking funding to extend the provision of an existing intervention for review of mental health medicines to:

a) be inclusive of all commonly prescribed medicines to older adults; and, b) tested in a diverse range of care home contexts, including in new socio-economically deprived geographical area away from the current research centre.

Objectives

This new funding will test whether the intervention can identify adverse events in those without mental illness and prevent pain, nausea, vision and dental problems in care homes without academic research support, in an area of greater socio-economic deprivation.

This project aims to:

- Record how the PADRe Profile works during usual care.
- Record any changes to care or prescriptions.

• Record any benefits and harms to residents.

• Estimate changes in quality of life and costs emanating from the intervention.

• Make recommendations as to how the PADRe Profile can be sustained during usual care.

The ADRe Profile improved care and prevented serious adverse events in care homes and

adult mental health teams in Abertawe Bro Morgannwg and Hywel dda UHBs, with the

support of the author (SJ) and her students (Jordan et al 2015, Jones et al 2016). We are

now extending the work to consider all medicines commonly prescribed in primary care:

amongst older adults receiving nursing home care, the prevalence of potentially

inappropriate prescribing is estimated to be 18.5%-82.6% (Dreischulte et al 2016).

Secondary research questions/objectives:

To document the extent to which the PADRe Profile fulfills its aims to:

• minimize adverse drug reactions without compromising the beneficial effects of medicines

• identify, monitor and ameliorate any possible adverse drug reactions associated with

medicines commonly prescribed in primary care

• ensure problems are communicated to pharmacists and prescribers efficiently

• provide practical detail for implementation

• facilitate shared decision-making with residents and within the multi-disciplinary team

Methods

6

Study Design

We will undertake an observational study. This will involve the following:

• an analysis of polypharmacy-related reports in the National Reporting and Learning

System (NRLS),

• a cognitive interview study with volunteers to review the PADRe Profile

• an eDelphi Study with experts to assess the modified PADRe Profile and

• a process evaluation (appendix – study flow diagram) to evaluate the practical use of

the PADRe Profile with 182 care home residents within 7 care homes in the ABUHB

area. This will involve debriefing interviews with care home nurses, a review of

residents' medical and nursing notes and interviews with stakeholders.

Process evaluation Study

Setting: we plan to recruit nursing homes from the area of the Aneurin Bevan University

Health Board.

Recruitment of nursing homes: care homes in AB UHB will be ordered by quality and safety

performance indicators from Health Board inspection. Homes from the lower, middle and

upper third tertials will be invited to participate. Those at the extremes will be approached

initially. Eligibility of nursing homes for entering the study is as follows:

Inclusion criteria:

7

- Providing residential or nursing care or both to >30 residents meeting inclusion criteria below.
- Willing to use the PADRe Profile in routine practice
- Staff aware of the Mental Capacity Act 2005, and willing to take informed consent.

Exclusion criteria:

- <30 residents meet the inclusion criteria
- Unwilling or unable to volunteer to undertake nurse-led medicines' monitoring
- Unwilling or unable to volunteer a nurse to act as site lead
- Not using the services of ABUHB primary care professionals.

Care homes will initially be sent an approach letter (appendix – care home approach letter) and they will be asked to reply with their decision by way of an email or telephone call. If, after 2 weeks, the care home does not reply, then a telephone call will be made to the care home for their decision. Where a home declines, the next in order will be approached. If a care home would like more information about the study, an appointment will be made with the Matron/Care Home Manager for the researcher and [name] to visit the home to discuss further.

Recruitment of care home residents: the study nurses and the matron/care home manager will decide which residents will be approached. A list of names of residents who are eligible to take part in the study will be drawn up by the matron/care home manager and the study nurses from medicines administration records. The study nurses should discuss the study

with the resident and if they are happy, can provide more information about the study and answer any questions the resident may have. The resident will have sufficient time to consider the information, discuss with others if they wish, and decide whether to participate. The resident's GP will also be informed of their participation in the study by way of a letter to the GP surgery (app 5b).

Obtaining consent from residents: Where residents have capacity they will be asked to provide written informed consent. The care home staff, preferably a registered nurse if one is available, the researcher or a GCP-trained research team member, fully cognisant of the Mental Capacity Act 2005 and trained in study procedures, will take consent from the residents (appendix – care home residents PIS and consent).

For those residents who have physical difficulty signing the consent form, they will provide verbal consent which will be witnessed by another person using the same form (appendix - care home residents PIS and consent). Verbal assent will be obtained in the presence of and countersigned by a literate, impartial and independent witness confirming that all the relevant information was provided to the research participant in an understandable manner. She/ he will read the written information supplied to the resident and be present throughout the entire informed consent discussion. After the written PIS and informed consent form and any other written information to be provided to the resident, is read and explained to the subject, and after the subject has orally consented to the subject's participation in the study, the witness will sign and personally date the consent form. By signing the consent form, the witness will attest that the information in the consent form

and any other written information was accurately explained to, and apparently understood by, the subject and that informed consent was freely given by the subject.

Where residents lack capacity to provide consent: According to the Mental Capacity Act, residents will be assumed to have capacity unless it is established that they lack capacity, all practicable steps having been made to help them do so. Many of the residents we will work with have cognitive impairment or dementia, even if there is no formal diagnosis. Where there is a concern that a resident lacks capacity to provide informed consent for themselves to participate in the study, the resident will be assessed for mental capacity by delegated individuals (i.e. the care home staff or the researcher and this will be documented). Where a resident does not have capacity, a 'consultee' will be consulted who will provide assent. If a family member is too frail to be approached, the consultee may be a friend or unpaid carer. The consultee will be provided with information about the study (appendix – consultee PIS_Consent), and they will be asked their advice regarding what the person's views would have been about participating in the research, if they had capacity to make the decision for themselves. They will sign a consultee declaration form (appendix – consultee PIS_Consent).

In the event that a consultee who has an unpaid or non-professional role in caring for the person cannot be identified, or is not willing to act, a nominated consultee will be appointed and consulted prior to including the resident in the study. This may be a member of staff at the care home. They too will sign the consultee declaration form (appendix – consultee PIS_Consent).

Inclusion criteria:

- Resident at the care home and expected to continue to live there for 1 year;
- Currently taking >3 prescribed medicines daily. Vitamin and nutritional supplements and
 moisturising skin preparations will not be counted as 'medicines'. PRN medicines given
 regularly, according to MAR charts, will be included. PRN medicines with no records of
 administration will not be counted.
- Willing and able to give informed, signed consent themselves, or where capacity is lacking, a consultee (as above) who is willing to give advice and assent to the resident participating.

Exclusion criteria

- Not well enough to participate, as screened by their nurses;
- Aged <18;
- Prescribed <4 medicines daily;
- Receiving active palliative care.

Recruitment of nurses to administer the PADRe Profile: Care home nurses (with or without NMC registration) will be invited to take part in the study by the Matron/Care Home Manager. One study lead nurse and one deputy lead nurse will be required and both will need to read a participant information sheet and sign a consent form with the researcher (appendix - Health professionals PIS and consent).

Inclusion criteria

- Working in care home, and expected to continue in employment for at least 6 months
- Qualified to administer medicines in the care home, trained in medicines' administration (DH 2016), either through NMC registration or appropriate qualifications, including QCF (Qualifications and Credit Framework 2012) and
- Willing and able to administer the PADRe Profile monthly

Exclusion criteria

- Not trained in medicines' administration
- Not undertaking medicines' administration
- Unwilling or unable to administer medication monitoring

Recruitment of community pharmacists; The researcher will initially ask the care home for the names and contact details of the pharmacists who are aligned to them. Community pharmacists will then be invited to take part in the study by the study Consultant Pharmacists (TB, JH) using a PIS and consent form (appendix – Health Professionals PIS and consent) by letter and email. Pharmacists will be required to sign a consent form.

Inclusion criteria:

- Aligned to a study care home and expected to continue employed as a pharmacist for a t least 6 months
- Willing and able to administer the PADRe Profile monthly

Recruitment of stakeholders for interviews: Study stakeholders (1 GP, 1 pharmacist and 1 consultee per care home) will be invited to carry out an interview by the researcher (appendix – Health professionals PIS and consent; appendix – consultee PIS and consent), verbally or by way of an email. All stakeholders who undertake an interview will be required to sign a consent form with the researcher undertaking the interview.

Inclusion criteria

- GP aligned to a participating nursing home and caring for the recruited participants
- A Community pharmacist aligned to a participating nursing home
- A person who is representing a resident who is participating in the study

Exclusion criteria

- Not involved with residents in care homes
- Unwilling to consent to audio recorded interview

Training the care home nurses and community pharmacists

Nurses will receive training including a video as well as comprehensive guidelines. The researcher will visit the care home and provide the training at a time and date convenient to the care home. Community pharmacists and pharmacists who act as a 'back-up' for the study will receive training from the study consultant pharmacist. The research team will remain available for further training and guidance as required throughout the study period.

Using the PADRe Profile with care home residents

Nurse leads in 7 homes will implement the PADRe Profile. They will need to complete the PADRe Profile with each of the residents (up to 26) at least every month, for 3 months as part of normal care. To do this, they will take some observations and ask some questions. All observations and questions are those that are sometimes used as part of normal care and are not invasive. The PADRe Profile checklist will help to determine clinical signs and symptoms of adverse drug reactions. At this time, the nurses will also be asked to complete a record/log/diary of using the PADRe Profile to record how it works during usual care. Both use of the PADRe Profile and recording how it works will take approximately 10 to 25 minutes per resident. We ask nurses that they try to carry out PADRe Profile completion with residents and using existing documentation at least every month or more frequently if medicines are changed. They will then pass it to the prescribers and pharmacists caring for the residents, along with the medication administration records.

Use of the quality of life questionnaire

At the start and end of the study, study nurses will fill in a quality of life questionnaire (the EQ-5D-5L) (Euroqol Group 2009) with the participating residents (EQ-5D-5L English; EQ-5D-5L Welsh https://euroqol.org/eq-5d-instruments/eq-5d-5l-about/). This consists of 5 'tick box' questions and will take approximately 5 minutes. This will determine whether the use of the PADRe Profile has improved (or not) the quality of life of the residents.

Undertaking reviews of the care home residents' nursing and medical notes

Consent for researchers to view patient records will have already been obtained from the residents when they consent to take part in the process evaluation at the start of the study.

The researcher will review these notes using a document review sheet (appendix – review

notes) before the start of the study and at the end of the study for evidence of use of the new PADRe Profile and any changes in care or outcomes of care.

Introductory and debriefing interviews with care home nurses

Before the implementation of the PADRe Profile, study nurses will be invited to take part in an introductory interview with the researcher who will ask them to discuss their views on medication monitoring and the potential of the PADRe Profile instrument. An interview guide will be used. Their knowledge of medications and adverse drug reactions will not be tested but rather, their views on these as well as their views on the PADRe Profile instrument to be used will be discussed. This interview will take place at the care home and will last approximately 30 minutes. Nurses will also receive a debriefing interview with the researcher at the end of month 2 of the implementation of the PADRe Profile (during its use) and at the end of month 3 of using the PADRe Profile. A separate interview guide will be used for debriefing the study nurses.

Undertaking interviews with the stakeholders

At the end of the study period where the PADRe Profile is used, the researcher will undertake qualitative interviews with stakeholders; 1 GP, 1 Community Pharmacist and 1 Resident Representative from each care home. They will be invited to discuss their experiences of participating in a study where the PADRe Profile is being used. This interview will take approximately 30 minutes and an interview guide will be used.

Study size

We shall introduce medicines' monitoring into 7 care homes, each with 26 residents prescribed >4 medicines (estimated ~90% residents (Jordan et al 2015). In previous work with participants acting as their own controls, de-prescribing occurred in 8.5% more participants (12.1% vs. 3.6%) when ADRe Profiles were used. We hypothesise that the new PADRe Profile will be twice as effective. Based on the reported intra-cluster coefficient (0.02) (Jordan et al 2015), 182 participants will detect this difference with 80% power & 5% significance, allowing for a 5% loss to follow up (Uitenbroek 1997, Killip et al 2004).

Analyses

Both quantitative and qualitative methods of analysis will be used and data will be triangulated.

Statistical analysis

Differences between before and after the intervention will be calculated for: problems addressed, prescription regimens, NHS use, and compared, adjusting for site (statistician AW). The impact of age, diagnoses, and medicines' use (numbers and types of medicines prescribed8) will be accounted. Resource use, costs, and health economic outcome measures will be described (JR).

Qualitative analysis

Interviews will be analysed by the team using the constant comparative method to identify predictors of successful adoption and any changes to the PADRe Profile, working

arrangements and oversight needed to embed use. This systematic, re-iterative method of comparing and contrasting emerging codes, categories and concepts ensures that theoretical perspectives are embedded in the description of change. Interviews will be coded, categorised, analysed and interpreted by at least two researchers and discussed at team meetings, with guidance and consistency checks.

Diaries/logs will also be analysed in association with interview transcripts.

Ethics

Permission to carry out this study will be given by an NHS Research Ethics Committee.

Following approval, any subsequent amendments will be communicated to the Ethics

Committee as well as the investigators, the study participants, and the trial registry.

Participation in the study is voluntary. All those participating will receive a participant information sheet (PIS) and will need to sign a consent form indicating their understanding of their role in the study. The researcher will also be available to discuss with the participants any questions that they may have.

All participants will be given sufficient time to decide whether they wish to take part. They will be informed that their participation in voluntary and that they are free to withdraw at any time without giving a reason for doing so. Those participants agreeing to be interviewed will be informed that their anonymised data and quotes may be used in any relevant publications.

Care home participants or their representatives will be informed that if they chose to withdraw from the study, their medical care or legal rights will not be affected. They will also be informed that

- sections of their care home health records may be looked at by individuals from Aneurin Bevan University Health Board, Cardiff and Swansea Universities and from regulatory authorities
- the completed PADRe Profile will be shared with the study pharmacist, together with a copy of their medication record
- their GP will be informed of their participation.

Declaration of interests: The chief investigator, principal investigator and all co-applicants and collaborators state they have no financial interests to declare in relation to the study and each study site.

Data storage

Case report forms (CRF) and audio devices will be stored in a locked cabinet in a locked office. The laptop/university computers used will be password protected. Any information transferred electronically will be anonymised.

All case notes will remain in the participant's organisation settings. Security & privacy of the case notes is maintained as per organisational routine practice.

We will ensure that signed consent forms will not be stored with participant data, including interview notes and transcripts. They are the only documents with identifiable data. They will be stored in a locked cabinet in a locked office for sole use of the CI.

Anonymised and de-identified data will be stored on password protected PCs for sole use of the researchers in locked offices for sole use of team members during the study. On completion, we shall store all current documents in locked tambour cupboards in AB UHB, and after 5 years documents will be sent to AB's archived files, into safe storage off site. AB UHB archives will be asked to destroy the data 5 years after the last publication from the study. This is to allow time for the research community to ask questions.

Data confidentiality

Participants will be given study numbers. Only the research assistant will keep a list linking numbers to care homes and names. This will be destroyed on completion of the study.

The study team will respect confidentiality of personal data and meet the requirements of the Data Protection Act, 1998. We will follow policies or guidance e.g. NHS Code of Confidentiality. The research team and staff are aware of and work to appropriate confidentiality standards. They have NHS backgrounds, and recognise the common law duty of confidentiality.

Any disclosures at interview will be treated in strict confidence. We shall avoid disclosure of attributable data in publications. Study numbers will be used throughout. Co-applicants will analyse redacted interview transcripts and field notes on password protected Swansea &

Cardiff University PCs. Most co-applicants are experienced qualitative researchers, with PhDs and academic publications. [name] will oversee the qualitative analysis. De-identified numerical data will be and analysed by [name] and [name] in their own secure offices. Quality of life (EQ-5D-5L), resource use and health economics data will be analysed by [name].

Confidentiality of de-identified personal data during data transfer via the University & UHB secure email network is assured. All pcs are password protected & require active log in. Additionally, the offices can only be accessed using own key. Only aggregated data will be reported. There are no plans to use the data outside the UK.

Dissemination

Letters will be sent to the participating care homes to inform them of the results of the study. Individual letters will also be sent to residents and their representatives. Other participants who have taken part in the study (for the e-DELPHI, the cognitive interviews and the stakeholder interviews - GP, Pharmacists) will receive results via postal letter or email.

This study will be a portfolio study for Health and Care Research Wales and will be recorded as such.

Translation of knowledge from evaluation of our implementation processes into steps and recommendations for establishing a national collaborative for ongoing quality improvement for prescribing in care homes. There is a developing community of practice involving

primary care professionals in Wales that would be a suitable mechanism for the spread of the innovation, in collaboration with Welsh Medicines Resource Centre (http://www.wemerec.org/Documents/Bulletins/optimisingmed2016online.pdf).

For example, the cost of hospitalization following a fall is \$25k (~£20,000) (Burns et al 2016). Preventing one hospitalisation per year would more than pay for the annual costs of a prescribing quality improvement programme in each health care organisation (Health Board / CCG).

Previously, nurses continued using the ADRe Profile after completion of the research. Nurses will receive training and comprehensive guidelines, and the research team will remain available. If the benefit of the PADRe Profile can be demonstrated to the satisfaction of participants, we expect that current policy drivers to improve medicines' management will promote continuation.

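### Care home staff choose which eligible residents are approached, and homes may have more eligible residents than the 26 places; a random approach order and a log would remove or expose that choice at little cost

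*Protocol*

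**What the plan says.** Under *Recruitment of care home residents*, the Protocol states that "the study nurses and the matron/care home manager will decide which residents will be approached". The same staff draw up the list of eligible residents from medicines administration records. No random, consecutive or approach-everyone rule follows. For homes, by contrast, *Recruitment of nursing homes* does set a sequence: homes are ranked, and a refusal leads to the next one.

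The numbers that bear on this are:

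- **Home eligibility:** "Providing residential or nursing care or both to >30 residents meeting inclusion criteria below", so at least 31.
- **Places:** nurse leads in 7 homes are to "complete the PADRe Profile with each of the residents (up to 26) at least every month". *Study size* uses 7 homes of 26.
- **Resident inclusion criteria:** one is "Willing and able to give informed, signed consent themselves, or where capacity is lacking, a consultee", so willingness is formally part of the count.
- **Resident exclusion criteria:** one is "Not well enough to participate, as screened by their nurses".

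The study nurses complete the EQ-5D-5L at the start and end, and the Protocol says of it: "This will determine whether the use of the PADRe Profile has improved (or not) the quality of life of the residents". *Statistical analysis* compares problems addressed, prescribing and NHS use before and after. It adjusts for site and takes account of age, diagnoses and medicines. Health economic measures are only to be described.

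**The concern.** The people choosing residents include those who deliver the intervention and those who score quality of life. They also know who is unwell at present and whose medicines are about to be changed. If they favour such residents, part of the later change would have happened anyway. If they favour residents who are stable and easy to include, the opposite can occur.

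Because residents act as their own controls, stable differences between those chosen and those left out largely cancel. Two things do not cancel: a temporary state at the start (regression to the mean) and a change already expected. Site, age, diagnoses and number or type of medicines do not capture either. The number of problems found, which bears on the aim of testing whether the Profile identifies adverse events, also depends directly on who is enrolled. Without a rule or a record of approaches, a reader cannot tell whether this bias was nil or near its limit.

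**Working it through.** **1. The plan's own figure.** 7 × 26 = 182. *Study size* gives earlier rates of 3.6% and 12.1% (8.5 points) and supposes PADRe to be twice as effective. I read that as 17 points, 3.6% to 20.6%. Two proportions, two-sided 5%, 80% power, no continuity correction:

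n = [1.96·√(2 × 0.121 × 0.879) + 0.84·√(0.036 × 0.964 + 0.206 × 0.794)]² / 0.17² ≈ 57 per group.

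Two groups: 114. Design effect 1 + 25 × 0.02 = 1.5, giving 171. Divided by 0.95: 180, close to the stated 182 (7 whole homes of 26). So 17 points is a fair reading of the hypothesised effect.

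**2. The surplus.** The Protocol gives only the minimum of 31. The figure of 40 is my assumption, to show the range.

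| Eligible | Without a place | Uptake at which the surplus vanishes |
|---|---|---|
| 31 | 5 (16%) | 26/31 = 84% or less |
| 40 (assumed) | 14 (35%) | 26/40 = 65% or less |

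**3. De-prescribing, extreme limits with no PADRe effect.** Suppose 3.6% of all eligible residents would be changed in the after period, staff foresee exactly who, and the before rate stays at 3.6%.

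- Upper limit = 3.6% × N/26: 4.3% at 31 and 5.5% at 40, a false gain of 0.7 or 1.9 points.
- Lower limit = 0%, because the expected number changed (1.1 of 31, 1.4 of 40) is smaller than the number left out. That is a false loss of 3.6 points.

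**4. Yardstick for de-prescribing.** 182 less 5% leaves 173 residents. Assume the design effect of 1.5 applies to the change.

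- Before and after independent: √(2 × 0.036 × 0.964 × 1.5/173) = 0.025, or 2.5 points.
- Correlation 0.5 (assumed): 2.5 × √0.5 ≈ 1.7 points.

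The false gain of 0.7 is below one standard error in both cases. The 1.9 exceeds it only at the assumed 40 with correlation 0.5. Against 17 points, the two gains are 0.7/17 = 4% and 1.9/17 = 11%.

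**5. EQ-5D-5L, regression to the mean.** With normal scores, the 26 lowest of 31 average 0.281 SD below the mean, and of 40 they average 0.559 SD below (simulation). With no true effect, apparent gain = (1 − r) × shift. At start-end correlation r = 0.5 (assumed) this is 0.14 SD at 31 and 0.28 SD at 40. At r = 0.9 it is 0.03 and 0.06. The standard error at r = 0.5 is √(2 × 0.5 × 1.5/173) = 0.093 SD. If staff judgement correlates only 0.5 with the start score, the ceilings halve to 0.07 and 0.14 SD. If staff judge a resident's usual state, the bias is about zero.

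**The case against.** **There may be no surplus.** A home cannot know who is willing before asking, so the count of more than 30 is probably made before consent. Exclusions are counted separately, and many residents will need a consultee. *Study size* puts about 90% of residents as qualifying on medicines, and 26/0.9 = 28.9, so the threshold may simply be headroom for reaching 26. This stands: a reader might infer that at least five willing residents per home are left out by choice, but the Protocol does not establish that.

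**The sentence may describe only the identification of eligible residents.** Nothing says that listed residents will be held back, and some staff gatekeeping is unavoidable: "Consent for researchers to view patient records will have already been obtained from the residents when they consent to take part". This is possible. But the wording gives staff the decision on whom to approach, and no other rule limits it.

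**The effect on the powered outcome is small.** This also stands. A reader might infer that selection could manufacture the hypothesised result. The Protocol's own figures do not support that, and the larger limits run downward, where they would hide a benefit.

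**Quality of life is only to be described.** True, although the Protocol also says the questionnaire will settle whether quality of life improved.

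**A random order removes only one discretionary step, and it takes time.** Also true. Staff would still draw up the list, screen fitness and may take consent. A further point is that *Data confidentiality* allows only the research assistant to hold the list linking numbers to names, so a code key held by the home would conflict with it. The fix has to respect that.

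**Conclusion.** The point holds as a design weakness that is cheap to repair. The Protocol gives staff the choice of whom to approach, and that choice determines enrolment in any home where refusals and exclusions do not bring the available residents down to 26.

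The resulting bias cannot be computed from the Protocol. Its direction is unknown and it may be zero. With perfect foresight by staff and no PADRe effect, the false de-prescribing gain is at most 0.7 points at the minimum home size. Quality of life is more exposed: its ceiling of 0.14 SD at 31 exceeds one standard error. That ceiling needs exact picking of the 26 worst and a start-end correlation of 0.5. All results for 40 eligible residents rest on an assumed home size.

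The case for change rests on the absence of a rule or visible record in an uncontrolled comparison, and not on any demonstrated distortion.

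**What to change.** In *Recruitment of care home residents*, replace staff choice with this rule. After the eligible list is drawn up and nurses have screened fitness, number the listed residents. Approach them in a random order supplied by the research team until 26 have consented. Approach everyone if 26 or fewer are available. Batches are acceptable, to leave time for consent and consultee contact. The consent and consultee safeguards stay as they are.

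The research team needs only list positions. Keep the numbered list temporarily in the home, separate from the study numbers, and say so alongside *Data confidentiality* so that the two statements agree.

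Log for each home the numbers eligible, screened out as not well enough, approached, declined, without a consultee, and not approached. If an appendix not shown already holds such a log, only the order needs adding.

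**Cost:** one random order and a one-page log for each of 7 homes, with no extra residents. Staff lose discretion over the order, and recruitment may be slightly slower. Selection through fitness screening remains, but the log would make it visible.
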